7.2. Hypoglycemia Induction Procedure and Justification

The most commonly used hypoglycemia insulin induction method cited in the literature [Nerموen] involves constant insulin infusion rates many-fold above normal basal infusion rates. As hepatic glucose production is determined by the glucagon to insulin ratio, this procedure may not create realistic circumstances for evaluating the effectiveness of glucagon in raising blood glucose. A predecessor study (XSGP-301), therefore, utilized a comparatively lower rate of insulin infusion at 1 to 2 times the normal basal rate, combined with push of an IV bolus dose of insulin derived from the subject's own self-reported glucose correction factor. About 30% of the procedures performed in Study XSGP-301 resulted in plasma glucose < 40 mg/dL (< 2.22 mmol/L). To get more precision in achieving a steady state of plasma glucose below 50 mg/dL (2.78 mmol/L), individual procedure data from the Study XSGP-301 were fitted to a model of insulin action allowing identification of opportunities for algorithm enhancements. The algorithm was modified accordingly and tested in the model of the procedures representing a broad spectrum of subjects, including the two extremes of insulin sensitivity that were associated with low plasma glucose in Study XSGP-303. The algorithm was further refined for use in the current study based on experiences in the XSGP-303 trial.

Hypoglycemia Induction Procedure

The evening before treatments subjects will be admitted to the CRC and follow the procedures described in Table 5.

Baseline Euglycemic Steady State

Prior to starting the hypoglycemia induction procedure, the subject must have stable plasma glucose for at least 30 minutes at 95 ± 20 mg/dL (75 to 115 mg/dL [4.17 to 6.38 mmol/L]) and a stable IV insulin infusion rate varying no more than $\pm 20\%$ during which plasma glucose must be measured at least every 15 ± 2 minutes.

Induction Start

For the induction, the starting plasma glucose level will be determined as the average of the last three YSI measurements taken during the baseline steady state period (i.e., start of baseline, next after 15 minutes, end of baseline after 30-minute baseline confirmation period). The following procedures will then be performed:

1. Subjects will continue the IV insulin infusion at the final rate of the baseline euglycemic steady state.
2. Subjects then will be given an initial IV bolus push dose of regular insulin diluted in saline:
 - a. The dose will be calculated as 75% of the dose estimated to reduce plasma glucose from the subject's starting plasma glucose level to 54 mg/dL (3 mmol/L) based on the subject's self-reported glucose correction factor. This dose will be referred to as "1 bolus (i.e., full bolus dose)" subsequently. The Investigator may use discretion to decrease the amount of the calculated bolus dose based upon the subject's insulin sensitivity factor. However, the Investigator is not allowed to increase the amount of the bolus dose.
 - b. Plasma glucose will be measured every 5 to 10 minutes, depending on the current plasma glucose value (see [Table 4](#)).
 - c. The first insulin adjustment will be made no earlier than 20 minutes after the initial bolus but will otherwise follow the directions for insulin adjustments shown in [Table 4](#).

The Investigator may override the insulin dosing algorithm at their discretion. Note: investigator does not have discretion to give bolus doses once plasma glucose is 65 mg/dL (3.3 mmol/L) or less (see numbers 3.b.i and 4.b.i below).

When plasma glucose is > 80 mg/dL (> 4.44 mmol/L), insulin adjustments should not be made more frequently than every 10 minutes. When plasma glucose is ≤ 80 mg/dL (≤ 4.44 mmol/L), the minimum time between adjustments to decrease, terminate or re-start insulin is either 10 or 5 minutes, as indicated in [Table 4](#).

1. While plasma glucose is > 80 mg/dL (> 4.4 mM/L):
 - a. Measure plasma glucose every 10 minutes.
 - b. When 10 minutes have passed from the last insulin dose adjustment:
 - i. Bolus: If the rate of plasma glucose decrease is < 0.15 mg/dL·min (< 0.01 mM/min), then an additional 1 bolus (full bolus dose) should be administered.

- ii. Infusion Rate: If the rate of plasma glucose decrease is $< 0.5 \text{ mg/dL}\cdot\text{min}$ ($< 0.03 \text{ mM/min}$), then the insulin infusion rate should be increased by 20%.
 2. While plasma glucose is 66 to 80 mg/dL (3.66-4.4 mM/L):
 - a. Measure plasma glucose every 5 minutes.
 - b. When 10 minutes have passed from the last insulin dose adjustment:
 - i. Bolus: If the rate of plasma glucose decrease is $< 0.15 \text{ mg/dL}\cdot\text{min}$ ($< 0.01 \text{ mM/min}$), then an additional 1/2 bolus (half-bolus dose) should be administered.
 - ii. Infusion Rate:
 - 1) If the rate of plasma glucose decrease is $< 0.33 \text{ mg/dL}\cdot\text{min}$ ($< 0.02 \text{ mM/min}$), then the insulin infusion rate should be increased by 20%.
 - 2) If the rate of plasma glucose decrease is $> 0.5 \text{ mg/dL}\cdot\text{min}$ ($> 0.03 \text{ mM/min}$), then the insulin infusion rate should be decreased by 20%.
 3. While plasma glucose is 61 to 65 mg/dL (3.39 to 3.61 mM):
 - a. Measure plasma glucose at least every 5 minutes.
 - b. When 10 minutes have passed from the last insulin dose adjustment:
 - i. Bolus: not allowed.
 - ii. Infusion Rate:
 - 1) If the rate of plasma glucose decrease is $< 0.25 \text{ mg/dL}\cdot\text{min}$ ($< 0.01 \text{ mM/min}$), then the insulin infusion rate should be increased by 20%.
 - 2) If the rate of plasma glucose decrease is $> 0.33 \text{ mg/dL}\cdot\text{min}$ ($> 0.02 \text{ mM/min}$), then the insulin infusion rate should be decreased by 20%.
 4. While plasma glucose is 54 to 60 mg/dL (3 to 3.33 mM):
 - a. Measure plasma glucose at least every 5 minutes.
 - b. When 10 minutes have passed from last insulin adjustment:
 - i. Bolus: not allowed.
 - ii. Infusion Rate:
 - 1) If the rate of plasma glucose decrease is $< 0.15 \text{ mg/dL}\cdot\text{min}$ ($< 0.008 \text{ mM/min}$), then the insulin infusion rate should be:
 - a. Increased by 20%, or

- b. Set at 120% of the previous rate if the infusion was previously set at the baseline rate or decreased by 50%.
Note: This escalation in rate can be performed every 5 minutes until the rate of decrease is $> 0.15 \text{ mg/dL}\cdot\text{hr}$ ($> 0.008 \text{ mM/hr}$)
 - 3) If the rate of plasma glucose decrease is greater than 0.25 up to 0.33 $\text{mg/dL}\cdot\text{min}$ ($>0.014 - 0.02 \text{ mM/min}$), then the insulin infusion rate should be decreased 20%.
 - 4) If the rate of plasma glucose decrease is greater than 0.33 up to 0.50 $\text{mg/dL}\cdot\text{min}$ ($>0.002 - 0.03 \text{ mM/min}$), then the insulin infusion rate should be decreased 50%.
 - 5) If the rate of plasma glucose decrease is $> 0.5 \text{ mg/dL}\cdot\text{min}$ ($> 0.03 \text{ mM/min}$), then the insulin infusion rate should be stopped. After 5 minutes, the insulin infusion should be restarted at the rate used at the end of the baseline period.
5. If the plasma glucose is $< 54 \text{ mg/dL}$ ($< 3 \text{ mM}$), then the IV insulin infusion should be returned to the baseline insulin infusion rate used at the end of the baseline period for 5 minutes, and then stopped.

Induction Termination

At any time, the induction procedure may be terminated at the Investigator's discretion. If the procedure is terminated, appropriate measures (oral or IV glucose) will be administered at the Investigator's discretion. If a subject exhibits signs of coma or convulsions, a IV bolus dose of dextrose will be given per standard of practice. Signs and symptoms should be monitored, and if the subject's condition fails to improve in a timely manner, additional dextrose or other medical interventions may be given at the Investigator's discretion.

Note: Study glucagon should NOT be administered as hypoglycemia rescue in this context.

Euglycemia will be confirmed and the subject should be medically stabilized per Investigator discretion before being released. The treatment visits should be rescheduled after a minimum 3-day wait.

If an SAE occurs during hypoglycemia induction, the procedure will end, and IV insulin will be safely withdrawn. Causality should be fully assessed by both the Investigator and the Sponsor.

Note: subjects will undergo a maximum of 4 hypoglycemia inductions in this study to achieve two successful procedures.

Table 4 Insulin Dose Adjustments

Plasma Glucose		Measurement Interval (minutes)	Target Rate of Plasma Glucose Decrease	Insulin Bolus Criteria	Insulin Basal Rate Adjustment Criteria
(mg/dL)	(mmol/L)				
> 80	> 4.44	10	> 0.5 mg/(dL·min) (> 0.03 mM/min)	If plasma glucose ↓ < 0.15 mg/(dL·min) (< 0.01 mM/min); give 1 bolus	If plasma glucose ↓ < 0.5 mg/dL·min (< 0.03 mM/min), ↑ 20% (10 min)
66-80	3.66-4.44	5	0.33-0.5 mg/(dL·min) (0.02-0.03 mM/min)	If plasma glucose ↓ < 0.15 mg/(dL·min) (< 0.01 mM/min); give ½ bolus	If plasma glucose ↓ < 0.33 mg/dL·min (< 0.02 mM/min), ↑ 20% (10 min)
					If plasma glucose ↓ > 0.5 mg/dL·min (> 0.03 mM/min), ↓ 20% (10 min)
61-65	3.39-3.61	5	0.25-0.33 mg/(dL·min) (0.014-0.02 mM/min)	Not allowed	If plasma glucose ↓ < 0.25 mg/dL·min (< 0.01 mM/min), ↑ 20% (10 min)
					If plasma glucose ↓ > 0.33 mg/dL·min (> 0.02 mM/min), ↓ 20% (10 min)
54-60	3-3.33	5	0.15-0.25 mg/(dL·min) (0.008-0.014 mM/min)	Not allowed	If plasma glucose ↓ < 0.15 mg/dL·min (< 0.008 mM/min), ↑ 20% (10 min); or If insulin infusion rate was previously set to baseline or the insulin infusion rate was ↓ by 50%, then set new insulin infusion rate at 120% of the prior rate (5 min) Note: This escalation in rate can be performed every 5 minutes until the rate of decrease is > 0.15 mg/dL·hr (> 0.008 mM/hr)
					If plasma glucose ↓ > 0.25 up to 0.33 mg/dL·min (> 0.014-0.02 mM/min), ↓ insulin infusion rate 20% (10 min) If plasma glucose ↓ > 0.33-0.50 mg/dL·min (> 0.02 up to 0.03 mM/min), ↓ insulin infusion rate 50% (5 min) If plasma glucose ↓ > 0.5 mg/dL·min (> 0.03 mM/min), Stop infusion; then set insulin infusion rate to baseline level (5 min)
< 54	< 3	5	0	Not allowed	Set to baseline level for 5 minutes, then Stop

↓=decrease, ↑=increase, min=minutes. [Note: if the plasma glucose decline is within the target range, keep the insulin infusion constant]

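### In the 54–60 mg/dL band, the note on 5-minute insulin escalation states its stopping rate per hour, while the trigger and target in the same row use the same numerals per minute

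*Protocol*

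**What the plan says.** Protocol Section 7.2 gives the insulin adjustment algorithm twice, as numbered steps and as Table 4. For plasma glucose of 54–60 mg/dL, Table 4 contains:

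- the trigger for an increase: "If plasma glucose ↓ < 0.15 mg/dL·min (< 0.008 mM/min), ↑ 20% (10 min); or"
- the target rate of fall: "0.15-0.25 mg/(dL·min) (0.008-0.014 mM/min"
- a note in the same cell as the trigger: "This escalation in rate can be performed every 5 minutes until the rate of decrease is" above a stated value, ending "until the rate of decrease is > 0.15 mg/dL·hr (> 0.008 mM/hr"
- the next criterion in the band: "If plasma glucose ↓ > 0.25 up to 0.33 mg/dL·min (> 0.014-0.02 mM/min), ↓ insulin infusion rate 20% (10 min"
- a table footnote: "if the plasma glucose decline is within the target range, keep the insulin infusion constant"

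Step 4 of the numbered text repeats the note, again per hour and in both unit systems. Every other rate of glucose fall in Section 7.2 and Table 4 is per minute. The section also says: "The Investigator may override the insulin dosing algorithm at their discretion". The SAP does not restate these rates; its Section 4.1 leaves the details of the induction procedure to the protocol.

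**The concern.** The note decides when the faster, 5-minute escalation must end, in the last glucose band before the 54 mg/dL threshold. It shares a cell with the trigger and has the same numerals, but its time unit differs. For a slow fall, staff therefore have two instructions that cannot both be followed: the note says the 5-minute steps are over, and the trigger says the fall is still too slow.

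At stake is whether inductions are run the same way throughout and reach the hypoglycemic steady state. Section 10.2.1.2 ends the procedure if steady state is not reached within 60 minutes of the first reading below 54 mg/dL. Section 7.2 allows at most four inductions per subject. Randomization comes before dosing, and SAP Section 6.5 counts a missing primary endpoint as a failure in the ITT and mITT analyses. A failed induction can therefore reach the primary analysis, although nothing in the documents suggests that this would fall more on one treatment than the other.

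**Working it through.** **Inputs**
- Note: 0.15 mg/dL per hour, 0.008 mM per hour (Section 7.2 step 4; Table 4).
- Trigger and lower end of target: 0.15 mg/dL per minute, 0.008 mM per minute (same row).
- Sampling in this band: every 5 minutes (Table 4), with a tolerance of ± 2 minutes (Section 7.1).
- Recording resolution: 0.1 mg/dL (Section 11.2).
- Conversion: 1 mmol/L = 18.0182 mg/dL (SAP Section 7.3).

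**1. Do the paired figures agree?** 0.15 / 18.0182 = 0.0083, which rounds to the stated 0.008. The mg/dL and mM figures agree within the note and within the trigger, so only the time unit is in conflict.

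**2. Size of the mismatch.** 0.15 / 60 = 0.0025 mg/dL per minute for the note, against 0.15 mg/dL per minute for the trigger. The ratio is 0.15 / 0.0025 = 60. Equivalently, the trigger is 0.15 × 60 = 9 mg/dL per hour.

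**3. Fall needed over one sampling interval**

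| Interval | Note (0.0025 per min) | Trigger (0.15 per min) |
|---|---|---|
| 5 min | 0.0125 mg/dL | 0.75 mg/dL |
| 7 min (upper tolerance) | 0.0175 mg/dL | 1.05 mg/dL |
| 10 min | 0.025 mg/dL | 1.5 mg/dL |

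Every entry for the note is below 0.1 mg/dL. At the note's rate a fall of 0.1 mg/dL takes 0.1 / 0.0025 = 40 minutes. The smallest recordable 5-minute fall is 0.1 / 5 = 0.02 mg/dL per minute, or 1.2 mg/dL per hour, which is 1.2 / 0.15 = 8 times the note's threshold. As written, the note therefore means that any recordable fall ends the 5-minute escalation.

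**4. Where the instructions conflict.** For falls between 0.0025 and 0.15 mg/dL per minute, the note has ended the 5-minute steps, the trigger still calls for an increase, and the fall is below target, so the footnote's hold rule does not apply. Over a 5-minute interval this covers the recordable falls 0.1, 0.2, ..., 0.7 mg/dL (0.7 / 5 = 0.14, still under 0.15; 0.8 / 5 = 0.16, over it).

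**5. What the conflict can change**
- If the ordinary increase, marked for 10-minute spacing in Table 4, continues after the note has stopped the 5-minute steps, then over 10 minutes there is one 20% step (× 1.20) instead of two (1.20 × 1.20 = 1.44). This assumes that the fall stays under 0.15 mg/dL per minute throughout.
- If staff take the note to end escalation altogether and hold the infusion, a fall continuing at 0.02 mg/dL per minute would take 6 / 0.02 = 300 minutes to go from 60 to 54 mg/dL. At 0.15 mg/dL per minute it would take 6 / 0.15 = 40 minutes.

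**6. Other unit mismatches in Section 7.2**
- For falls above 0.33 and up to 0.50 mg/dL per minute, the numbered text gives a lower bound of 0.002 mM per minute and Table 4 gives 0.02. The conversion is 0.33 / 18.0182 = 0.018.
- The remark limiting bolus doses pairs 65 mg/dL with 3.3 mmol/L, whereas Table 4 and Table 8 pair it with 3.61. The conversion is 65 / 18.0182 = 3.61, while 3.3 × 18.0182 = 59.5 mg/dL.

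**The case against.** The strongest case on the other side is that this is probably a clerical slip with little effect. The numerals match and all the other rates are per minute, so a site might well notice it. The note is permissive. In Table 4 it follows the branch for an infusion previously set to baseline or halved, so it can be read as confined to that branch. Investigators may override the algorithm, and Section 7.1 provides for sponsor staff to follow inductions in near real time.

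Much of this stands as a limit on the consequence. It does not remove the contradiction: a slip is an inference that only the sponsor can confirm, and both override and monitoring need one stated rule to work from. Nor is the unit an artefact of one damaged table cell, since it appears in the text and the table and in both unit systems.

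Two stronger readings are tempting, and the documents do not support them.

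- *That the note drives too much insulin.* The literal per-hour rule ends the 5-minute steps sooner. Read per minute, it would end them at the lower end of the row's target. Neither reading allows escalation beyond the target.
- *That it biases the comparison through insulin on board at dosing.* Below 54 mg/dL the infusion returns to the baseline rate for 5 minutes and then stops, and dosing requires a confirmed steady state. The trial is a within-subject crossover with randomization stratified by site, so a site's habitual reading would tend to apply in both periods. No direction or size of bias can be derived from the documents.

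**Conclusion.** The protocol contradicts itself on a decision threshold in an operative insulin rule. The note and the trigger differ by a factor of exactly 60, and the note's threshold cannot be resolved at the sampling interval. This rests on reading the dot in the rate units as "per", as the whole algorithm requires, and on computing the rate of fall from readings 5 to 10 minutes apart; Section 7.2 does not state the interval, but the conclusion is the same throughout that range.

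The practical effect is smaller than the ratio suggests. Taken literally, the note gives fewer or later increases. The difference is mainly one of 5-minute against 10-minute spacing of the same 20% step, or a longer delay if staff hold the infusion. It concerns the consistency and success of induction. No bias in the treatment comparison, and no change to power or alpha, is shown. The correction should be made, but it does not call the design or the primary analysis into question.

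**What to change.** Reconcile the time unit in the escalation note with the trigger and target of the same row, in both Section 7.2 step 4 and Table 4. The sponsor should state which unit applies; this review does not choose one. It would help to say also whether the note covers only the branch for an infusion previously set to baseline or halved. Then notify sites in writing.

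In the same correction, reconcile 0.002 with 0.02 mM per minute (numbered text against Table 4), and 3.3 with 3.61 mmol/L for 65 mg/dL (the remark on bolus doses against Table 4 and Table 8).

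The cost is a short protocol correction and a site memo, with the ethics review that Section 17.1 requires for protocol modifications. The SAP, the sample size and the primary analysis need no change on this account.

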7.3. Interruption and Termination of Dosing

As described in Section 7.1 , administration of study glucagon is only permitted if a subject meets the criteria for a hypoglycemic steady state. Administration of study glucagon to a subject not in a hypoglycemic steady state will be deemed a major protocol violation.

At 30 minutes post-glucagon administration, if a subject fails to achieve an increase of plasma glucose of at least 20 mg/dL (1.11 mmol/L), appropriate measures (oral or IV glucose) will be taken at the Investigator's discretion.

Post-administration of study glucagon, if a subject exhibits signs of coma or convulsions, a IV bolus dose of dextrose will be given per standard of practice. Signs and symptoms should be monitored, and if the subject's condition fails to improve in a timely manner, additional dextrose or other medical interventions may be given at the Investigator's discretion.

Note: A second dose of study glucagon should NOT be administered as hypoglycemia rescue in this context.

Euglycemia will be confirmed and the subject should be medically stabilized per Investigator discretion before being released. If applicable, completion of a subsequent treatment visit will be at the discretion of the Investigator in consultation with the Medical Monitor.

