5. Subcutaneous administration of the study drug will be made to the abdomen around the umbilicus as per [Section 9.3.3](#). Clock time of study drug administration will be recorded in the source documents. After study drug injection, the study product will be disposed in a location away from the subject in a manner that maintains the blind. After disposal, the blindfold and headphones will be removed from the subject.
6. Following study drug administration, plasma glucose will be measured every 5 ± 2 minutes through 90 minutes, and every 30 ± 2 minutes thereafter through 180 minutes post-dosing.

7. At 180 minutes post-dosing, the subject will resume insulin therapy and be given a meal as per the standard practice at each site. The subject can be discharged from the clinic if their plasma glucose is >100 mg/dL (> 5.55 mmol/L) and the subject is deemed medically stable.
8. After study drug administration and before 180 minutes post-dosing, if rising glucose levels are observed and if deemed medically necessary, insulin therapy or other medical intervention may be initiated by the Investigator.
 - a. Such intervention is not recommended to occur before 90 minutes post-dosing of study drug.
 - b. Plasma glucose data and assessments of neuroglycopenic symptoms will be censored after the time of intervention, per the statistical analysis plan.
 - c. These interventions (such as insulin, carbohydrates, or a meal) prior to 180 minutes post study drug administration should be captured in the source documents, and further glucose measurements may be performed at the discretion of the Investigator.

Hypoglycemia Symptom Assessments

Subjects will complete a questionnaire regarding severity of hypoglycemia symptoms ([Appendix 1](#)) at the following time points:

1. Just before the IV bolus push dose of insulin is given at the start of the hypoglycemia induction procedure (baseline),
2. Every time blood is drawn for evaluation of plasma glucose concentration during the induction procedure,
3. Just before study drug is administered,
4. Every 5 ± 2 minutes after glucagon is administered until 90 minutes post-dosing, and every 30 minutes (coinciding with plasma glucose measurements) between 90 and 180 minutes post study drug administration.

Local Tolerability and Adverse Events

Local tolerability and AEs will be assessed as follows:

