13.3. Primary Endpoint

The primary endpoint comparison will be performed using both the Intention to Treat (ITT) and the per-protocol (PP) populations. The evaluable set for the PP population will be defined as all randomized subjects who, during both study periods, successfully complete the insulin induction procedure, fulfill the criteria for having achieved a hypoglycemic steady state, and successfully receive a dose of both study drugs (G-Pen followed by GlucaGen Hypokit, or GlucaGen Hypokit followed by G-Pen). For analysis of the primary endpoint, a failure for the study treatment (G Pen or GlucaGen Hypokit) will be recorded if the increase in plasma glucose remains < 20 mg/dL (< 1.11 mmol/L) throughout the 0- to 30-minute period from injection of study drug, while a success is defined as an increase in plasma glucose ≥ 20 mg/dL (≥ 1.11 mmol/L) in subjects from a state of insulin-induced hypoglycemia within the 0- to 30-minute period from injection of study drug.

Non-inferiority will be established based on the calculated 95% confidence interval for the difference in failure rates between G-Pen and GlucaGen Hypokit. Non-inferiority will be declared if the upper limit of the 95% confidence interval for the difference in failure rates is $\leq 5\%$; where the absolute failure rate of G-Pen treatment is $\leq 5\%$.

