5.3.6.1 Primary Endpoint

Positive Plasma Glucose Response 1 (PGR1)

Positive Plasma Glucose Response 1 (PGR1) is defined as reaching a plasma glucose concentration ≥ 70 mg/dL (≥ 3.88 mmol/L) within 30 minutes of study drug injection (actual time). (The baseline plasma glucose is the blood glucose reading immediately before study drug dosing.)

Positive Plasma Glucose Response 2 (PGR2)

Positive Plasma Glucose Response 2 (PGR2) is defined as reaching an increase in plasma glucose concentration ≥ 20 mg/dL (≥ 1.11 mmol/L) within 30 minutes of study drug injection (actual time).

Positive Plasma Glucose Response (PGR)

For the primary endpoint, Positive Plasma Glucose Response (PGR) is defined as reaching Positive Plasma Glucose Response 1 (PGR1) **or** Positive Plasma Glucose Response 2 (PGR2).

For the primary endpoint, treatment groups will be compared for rates of achieving a positive plasma glucose response. The comparison will be performed using Intention to Treat (ITT), Modified Intent-to-Treat (mITT) and the Per-Protocol (PP) populations. Risk difference in rates of failing to achieve Positive Plasma Glucose Response (PGR) will be assessed for G-Pen versus GlucaGen Hypokit used as reference and the associated 95% CIs presented.

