6.5 Analysis of Primary Endpoint

The primary endpoint analysis will be based on the risk difference in rates of failing to achieve Positive Plasma Glucose Response (PGR) of G-Pen versus GlucaGen Hypokit and a 95% CI will be calculated. Non-inferiority will be declared if the upper limit of the 95% confidence interval for the difference in failure rates is $\leq 5\%$; where the absolute failure rate of G-Pen treatment is $\leq 5\%$. This analysis will be repeated for ITT, mITT and PP populations.

Subjects who are missing the primary endpoint for a study treatment will be considered as having a failure in the primary analysis for that treatment administration. This imputation will be conducted for both the ITT and the mITT populations. If a subject received the same two treatment administrations for both periods (Period 1 and Period 2), only the visit with the planned treatment received will be included in the primary analysis and the subject will be considered a failure in the primary analysis for the for unreceived treatment administration (ITT, mITT). For all other analyses, data will be included for only the planned treatment received in those analyses.

A sensitivity analysis will be performed for where all missing data will be considered a success and the same analysis as above completed.

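### Under the SAP, a glucose reading raised by rescue dextrose inside the 30-minute window can count as a primary success, because no rule scores rescue and censoring is limited to restarted insulin

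*Protocol*

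**What the plan says.** **Rescue.** Protocol 7.3 has two routes after dosing.
- For collapse, with no time limit: "Post-administration of study glucagon, if a subject exhibits signs of coma or convulsions, a IV bolus dose of dextrose will be given".
- For glucose non-response, at the end of the window: "At 30 minutes post-glucagon administration, if a subject fails to achieve an increase of plasma glucose of at least 20 mg/dL", oral or IV glucose follows at the investigator's discretion.

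**Endpoint.** SAP 5.3.6.1 defines PGR1 as a glucose of at least 70 mg/dL and PGR2 as a rise of at least 20 mg/dL. Either one makes a positive response (PGR) if it occurs "within 30 minutes of study drug injection (actual time" being used. Protocol 13.3 instead defines failure by the rise alone, if it stays below 20 mg/dL "throughout the 0- to 30-minute period from injection of study drug". Neither definition mentions rescue.

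**Censoring.** Protocol 10.2.1.2, in the steps for preparing and giving study drug, states: "Plasma glucose data and assessments of neuroglycopenic symptoms will be censored after the time of intervention, per the statistical analysis plan". The interventions it covers include insulin, other medical intervention, carbohydrates and a meal. SAP 4.1 quotes this text but limits the censoring to cases where insulin is restarted before 180 minutes. SAP 5.3.6.2.1 likewise sets values to missing only after an insulin start.

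**Missing data.** SAP 6.5 counts a missing primary endpoint as a failure (ITT and mITT) and adds: "A sensitivity analysis will be performed for where all missing data will be considered a success".

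**Precedence.** Protocol 13.1 and SAP section 2 both put the SAP above the protocol.

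**The concern.** Needing dextrose for coma or convulsions before any glucose response is a plain failure of a hypoglycemia rescue drug. Glucose is sampled every 5 minutes, so readings taken after the dextrose can fall inside the window. A reading that crosses a threshold is then credited to the study drug. The same crediting reaches PGR1, PGR2, positive treatment response and time to PGR.

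The decision to rescue is made by staff who know the treatment, since only the subject is blinded (Protocol 9.2). The plan expects success rates approaching 100%. At such low failure counts, non-inferiority can turn on a single subject.

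**Working it through.** **Step 1: follow one subject through the rules.** Suppose a subject has met neither threshold, receives dextrose at 10 minutes for a convulsion, and has a reading at or above 70 mg/dL by 30 minutes. The times are illustrative.

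| Rule applied | Post-dextrose reading | Main analysis (ITT, mITT) | Sensitivity analysis |
|---|---|---|---|
| SAP 4.1 and 5.3.6.2.1 (insulin only) | kept | success | success |
| Protocol 10.2.1.2 (any intervention) | censored, so missing | failure | success |

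The second row assumes that censored readings leave the endpoint missing, as SAP 5.3.6.2.1 does after insulin. No row gives a failure in both analyses. SAP 4.1 literally places the censoring after drug administration; I take this to mean the restarted insulin.

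**Step 2: inputs for the size.**
- N = 122 randomized and 111 evaluable (SAP 4.2). The plan's inflation reproduces as 111 × 1.10 = 122.1. The 111 itself cannot be reproduced because no odds-ratio margin is given, but this point does not depend on it.
- Criteria: upper 95% limit of the failure-rate difference at most 5%, and G-Pen failure rate at most 5% (SAP 6.5).
- Interval: two-sample Wald, as the SAP Appendix 2 risk-difference code produces.

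**Step 3: formula.** With a G-Pen failures and b GlucaGen failures, p1 = a/N and p2 = b/N:

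upper = (p1 − p2) + 1.96 × √[p1(1 − p1)/N + p2(1 − p2)/N]

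For a = 3, b = 0, N = 122: p1 = 0.02459, SE = √(0.02459 × 0.97541/122) = 0.01402, upper = 0.02459 + 0.02748 = 5.21%.

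**Step 4: results.**

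| N | GlucaGen failures | G-Pen failures | Upper limit | Non-inferior |
|---|---|---|---|---|
| 122 | 0 | 2 | 3.89% | yes |
| 122 | 0 | 3 | 5.21% | no |
| 122 | 1 | 3 | 4.82% | yes |
| 122 | 1 | 4 | 6.00% | no |
| 122 | 2 | 3 | 4.37% | yes |
| 122 | 2 | 4 | 5.52% | no |
| 111 | 0 | 2 | 4.28% | yes |
| 111 | 0 | 3 | 5.72% | no |

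One subject is 1/122 = 0.82 percentage points.

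**Step 5: direction.** Suppose the true counts are 3 G-Pen and 0 GlucaGen failures. Crediting one rescued G-Pen subject moves the limit from 5.21% to 3.89%, a false claim of non-inferiority. Now suppose they are 3 and 1. Crediting the rescued GlucaGen subject moves it from 4.82% to 5.21%, a lost claim.

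**Step 6: rescue trigger against endpoint.** The 30-minute trigger is a rise below 20 mg/dL; PGR also accepts 70 mg/dL. Dosing requires a glucose below 54 mg/dL. From a baseline b, reaching 70 is a rise of 70 − b, which is under 20 when b exceeds 50. A subject going from 53 to 71 mg/dL (rise 18) is a PGR success who also meets the trigger.

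**The case against.** The best defence joins two rules: the protocol censors glucose after an intervention, and SAP 6.5 fails a missing endpoint. Together they would make a rescued subject a failure. This does not hold under the SAP, which limits censoring to insulin and takes precedence. The protocol clause is also introduced for rising glucose, not for collapse. Even if applied, it leaves the subject a success in the sensitivity analysis. Treating missing as success is an ordinary best-case bound, but a rescued subject's outcome is known and does not belong in it.

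The route is also narrow, and that stands. Rescue for non-response comes only at 30 minutes, so coma or convulsions is the one trigger specified inside the window. Dosing requires a glucose and an 8-minute extrapolated value of at least 42 mg/dL with insulin stopped, and Protocol 7.1 expects that range to avoid impaired consciousness. An event would probably also surface in the SAE listings, though that does not correct the endpoint.

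A reader might infer three stronger things that the documents do not support:
- *Every rescued subject is scored as a success of a drug that failed.* A reading must cross a threshold by 30 minutes, no dextrose dose is stated from which to predict that, and the subject may have met PGR before the event.
- *Crediting rescue in either arm makes the arms look alike.* Step 5 shows that it works against non-inferiority after GlucaGen.
- *The absolute 5% limit (6/122 = 4.92%, 7/122 = 5.74%) is the critical boundary.* With 6 G-Pen failures the upper limit is 5.43% against 6 GlucaGen failures and 4.82% against 7. That boundary matters only when GlucaGen has at least 7 failures; below that the confidence limit binds first.

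The trigger mismatch is secondary. The trigger agrees with the failure definition in Protocol 13.3, action at 30 minutes cannot change a response already recorded, and a safety trigger need not equal an efficacy endpoint.

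**Conclusion.** The concern holds in a conditional form. Under the controlling SAP, dextrose given inside the window before any positive response does not stop a later reading in that window from scoring as a primary success. This is a wrong score produced by stated rules, and the protocol and SAP censoring texts disagree on the same event.

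The expected number of such subjects is small, and the documents give no count. The consequence of one is not small: it can reverse the conclusion when true failures sit at the boundary, for example 3 G-Pen against 0 GlucaGen, or 4 against 1. The bias favours G-Pen only when the rescue follows G-Pen. These figures assume the Appendix 2 Wald interval and all 122 subjects scored for both treatments; the 111-subject rows show the same pattern.

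**What to change.** 1. Add to SAP 5.3.6.1 and 6.5: any oral or IV glucose, dextrose or other glucose-raising treatment given after study drug and before a positive plasma glucose response makes that treatment period a failure for PGR, PGR1 and PGR2. Post-rescue glucose and symptom readings do not count towards positive treatment response. Both rules apply in the main and the sensitivity analyses. Post-rescue readings do not count as events in time to PGR.
2. Make the censoring text in Protocol 10.2.1.2, SAP 4.1 and SAP 5.3.6.2.1 agree on which interventions it covers.
3. Confirm that rescue clock times reach the database. Protocol 10.2.1.2 asks only that interventions be captured in source documents.
4. Ask the clinical team to reconcile the 30-minute trigger in Protocol 7.3 with the differing endpoint definitions (Protocol 13.3 against Protocol 5.3.1, SAP 3.3.1 and SAP 5.3.6.1). No rescue rule is proposed here.

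Cost: SAP wording before database lock, possibly one added time field, and failure rates that may be slightly less favourable. The sample size does not change. Protocol 13.1 requires an amendment for major changes to the primary endpoint or its analysis, so the sponsor should decide whether item 1 is one.
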